### 13.1 Clinical data system management

Data will be managed at Indiana University. Data will be collected and managed with REDCap (Research Electronic Data Capture), an established, secure, web-based data capture and management tool developed at Vanderbilt University and supported by the bioinformatics team at IU. The security of the database will be maintained by the use of dedicated password protected encrypted computers with multiple private backups (daily, weekly, and monthly including on- and off-site storage for protection against disaster).

### 13.2 Data retention

All clinical investigation records and reports must remain on file at the clinical investigation centers for the minimum time given by the national legislation.

The investigator must contact Medela AG before destruction of any records and reports related to the clinical investigation. Medela AG must be informed if the investigator plans to leave the

clinical investigation site. In such case the site must name a new contact person before the investigator parts from the clinical investigation site.

Medela AG will retain the Trial Master File (TMF) according to national legislation and Medela AG Standard Operating Procedure (SOPs).

Medela AG is responsible for instructing all involved parties to maintain clinical investigation records according to national regulations.

### 14 Monitoring

Monitoring will be performed by Medela AG or by Medela AG designees and the PI to ensure that the investigator and the clinical investigation team conducts the clinical investigation in accordance with the CIP, Declaration of Helsinki, ISO 14155:2011(E), ICH-GCP and applicable regulations to ensure adequate protection of the rights, safety and wellbeing of subjects and the quality and integrity of the resulting data.

The monitor will verify that records on the clinical investigation conduct and data collection are complete and present, and that the device accountability is complete

### **15 Statistical Analysis**

Descriptive statistics will characterize the group of individuals recruited into the study. Categorical variables will be reported and proportions while continuous variables will be reported as mean and standard deviation or median and interquartile range as appropriate. The primary outcome and other categorical secondary outcomes will be reported as proportions with 95% confidence intervals. As this is a two-site trial, subgroup analyses will be performed by site as well as body mass index.

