| Primary endpoint   | Patient centered outcomes   |  |  |  |
| y 1   | 
 
Pain scores (scale of 0 - 10) at discharge and
 
  |  |  |  |
|  | postoperative day 30 (+/-2 days)  |  |  |  |
|  | Patient satisfaction scores (scale of 0 - 10) at discharge  |  |  |  |
|  | and postoperative day 30 (+/- 2 days)   |  |  |  |
|  | • Patient satisfaction with aesthetic appearance (scale of 0  |  |  |  |
|  | - 10) at postoperative day 30 (+/- 2 days)  |  |  |  |
| Secondary endpoint   | Efficacy outcome  |  |  |  |
|  | • Composite wound complication including wound infection,   |  |  |  |
|  | would separation, seroma, antibiotics prescribed for  |  |  |  |
|  | presumed SSI within 30 days (+/- 2 days)  |  |  |  |
|  | Safety outcomes:  |  |  |  |
|  | • Skin blistering, allergic reaction, wound bleeding  |  |  |  |
| Study device   | Invia Motion  |  |  |  |
|  |   |  |  |  |
| Reference device   | Not applicable  |  |  |  |
|  |   |  |  |  |

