# 8.2 Study hypotheses

We test the hypothesis that the Medela INVIA Motion prophylactic NPWT system will be feasibly used at cesarean delivery with significant patient satisfaction.

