# 8.3 Claims to verify

Feasibility of the Medela INVIA Motion prophylactic NPWT system at cesarean delivery with significant patient satisfaction.

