# 8.6 Primary Endpoint

Patient centered outcomes

- Patient satisfaction scores (scale of 0 10) at discharge and postoperative day 30 (+/- 2 days)
- Pain scores (scale of 0 10) at discharge, at removal and postoperative day 30 (+/-2 days)
- Patient satisfaction with aesthetic appearance (scale of 0 10) at postoperative day 30 (+/- 2 days)

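### Section 15 reports the primary outcome as proportions, but every primary measure is a 0-10 score and no cut-off is given

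*Combined protocol and SAP*

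**What the plan says.** **Endpoints.** Section 8.6 lists three primary measures, each scored from 0 to 10:

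- satisfaction: "Patient satisfaction scores (scale of 0 10) at discharge and postoperative day 30 (+/- 2 days";
- pain: "at discharge, at removal and postoperative day 30 (+/-2 days";
- appearance: "Patient satisfaction with aesthetic appearance (scale of 0 10) at postoperative day 30 (+/- 2 days".

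The synopsis lists the same three measures, but its pain line begins "Pain scores (scale of 0 - 10) at discharge and" and continues to day 30, without the removal time point.

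**Analysis.** Section 15 first says that "continuous variables will be reported as mean and standard deviation or median and interquartile range as appropriate". The next sentence is "The primary outcome and other categorical secondary outcomes will be reported as proportions with 95% confidence intervals". The words *other categorical* place the primary outcome among the categorical variables.

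**Claims.** Section 8.2 states: "We test the hypothesis that the Medela INVIA Motion prophylactic NPWT system will be feasibly used at cesarean delivery with significant patient satisfaction". Section 8.3 repeats this as the claim to verify: "Feasibility of the Medela INVIA Motion prophylactic NPWT system at cesarean delivery with significant patient satisfaction". Neither section says what level of satisfaction would count as significant.

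**The concern.** A proportion needs a yes/no variable. A 0-10 score becomes one only through a cut-off, and none is stated for any score. The analysis sentence also speaks of one primary outcome, while the endpoint lists contain five or six score-by-time summaries.

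If the sentence is followed, whoever analyses the data must choose the cut-offs, possibly with the scores in view. The study is single-arm, and satisfaction is one of its stated claims, so the headline percentage would depend on that choice. Power and type I error are not at stake: section 15 contains no test and no success threshold, and feasible use is a separate part of the hypothesis.

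**Working it through.** **1. Is there a cut-off anywhere?** The synopsis and sections 8.2 to 8.6.1, 10.5, 10.5.2, 15 and 15.1 were read for one. None gives a cut-off or responder definition for a score. The only numeric outcome threshold is in section 8.4 (below 10%), and it concerns device-related adverse events.

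**2. How many primary summaries are there?**

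- Synopsis: pain × 2 + satisfaction × 2 + appearance × 1 = 5.
- Section 8.6: pain × 3 + satisfaction × 2 + appearance × 1 = 6.

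**3. How much would the cut-off matter?** There is no figure in the plan to reproduce: section 15.1 gives n = 30 without a formal calculation, and no mean or SD is stated. The following is an illustration under assumptions. Scores are modelled as a normal variable rounded to whole points, with mass beyond the ends placed at 0 or 10. Its parameters are solved so that the resulting 0-10 score has the stated mean and SD.

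Satisfaction, share at or above each cut-off:

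| Assumed mean, SD | ≥7 | ≥8 | ≥9 | One-point falls (points) | Fall from ≥7 to ≥9 (points) |
|---|---|---|---|---|---|
| 7.5, 1.5 | 74.9% | 50.8% | 26.5% | 24.0, 24.3 | 48.3 |
| 7.5, 2 | 69.8% | 53.1% | 35.8% | 16.7, 17.3 | 34.0 |
| 8, 1.5 | 83.5% | 64.2% | 40.2% | 19.3, 24.0 | 43.3 |
| 8, 2 | 77.3% | 63.9% | 48.5% | 13.4, 15.4 | 28.8 |
| 8.5, 1.5 | 88.9% | 75.3% | 56.0% | 13.5, 19.3 | 32.8 |
| 8.5, 2 | 83.2% | 74.0% | 62.7% | 9.2, 11.3 | 20.6 |

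Falls are taken before rounding.

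Take mean 8 and SD 2 with 30 patients. Exact (Clopper-Pearson) 95% intervals are:

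- ≥7: 0.773 × 30 ≈ 23, so 23/30 = 77% (57.7% to 90.1%);
- ≥8: 0.639 × 30 ≈ 19, so 19/30 = 63% (43.9% to 80.1%);
- ≥9: 0.485 × 30 ≈ 15, so 15/30 = 50% (31.3% to 68.7%).

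Pain, share at or below each cut-off:

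| Assumed mean, SD | ≤2 | ≤3 | ≤4 |
|---|---|---|---|
| 2, 1.5 | 64.2% | 83.5% | 94.3% |
| 2, 2 | 63.9% | 77.3% | 87.4% |
| 3, 1.5 | 37.2% | 63.3% | 84.3% |
| 3, 2 | 42.2% | 60.7% | 77.1% |
| 4, 1.5 | 15.5% | 36.8% | 63.3% |
| 4, 2 | 23.2% | 40.6% | 60.1% |

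One-point changes run from 10.0 to 26.5 points.

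**4. What does a summary without a cut-off give?** The 95% CI half-width for a mean is t(0.975, 29) × SD / √30 = 2.045 / 5.477 × SD = 0.373 × SD. That is 0.56 points at SD 1.5 and 0.75 points at SD 2, if all 30 patients are scored. Simulated coverage of this interval (200,000 samples per setting) was 93.6% to 94.9% for the satisfaction settings and 94.5% to 95.0% for the pain settings, so it behaves adequately despite the bounded scale.

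**The case against.** The strongest reply is that this is a drafting slip in a small descriptive series. The measures, scales and visit windows are all given, and only the form of the summary is unclear. The mean/median sentence may cover the scores, in which case a summary without a cut-off already exists. Or it may describe only the recruited group, in which case the two sentences do not conflict. The share at each of the 11 score values could also be tabulated without any cut-off.

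Part of this stands. The wording may well be carried over from a study with a binary outcome: section 7.2 speaks of infection rates against standard care, and section 10.2 of study groups. Intent to dichotomise is not shown. But neither reading of the mean/median sentence rescues the plan. The next sentence names the primary outcome and assigns it to proportions, and tabulation of all 11 values is not what the plan says.

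Three further points are fair:

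- The illustration depends on its model. A plain rounded normal with mean 8 and SD 2, not matched to the bounded scale, gives about 60% at ≥8 and 40% at ≥9, instead of 63.9% and 48.5%. Both show strong dependence on the cut-off.
- Under the satisfaction settings, about 10% to 50% of patients would score the maximum of 10, so a mean alone would describe the data poorly. The median and full distribution should accompany it.
- Section 10.4 has the dressing taken off on the day of discharge, or on day 7 in longer stays, so pain at removal and at discharge will often coincide. The mismatch between section 8.6 and the synopsis is real but minor.

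**Conclusion.** The concern holds. Section 15 prescribes proportions for a primary outcome made up entirely of 0-10 scores, and this cannot be carried out without a cut-off that the plan does not state. The absence of a criterion for significant satisfaction in sections 8.2 and 8.3 leaves the same gap in the claim.

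Under the assumed score distributions, a one-point change in cut-off moves the reported share by about 9 to 24 points for satisfaction and 10 to 27 points for pain. Moving from ≥7 to ≥9 lowers the satisfied share by 21 to 48 points. These sizes rest on assumed means, SDs and distribution shape; that the result depends on an unstated choice does not. The consequence is confined to how satisfaction, pain and appearance are summarised and described. It should be fixed, but it does not threaten the study.

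**What to change.** Replace the sentence in section 15 with wording such as:

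> Each 0-10 score is summarised at each time point by its mean (SD) with a 95% CI, with the median (IQR) and the full distribution also shown. Binary secondary outcomes are reported as proportions with exact 95% CIs.

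In addition:

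- If any proportion of a score is kept, state its cut-off for each score before any scores are reviewed.
- Either name one score and time point as the lead summary, or say that all are reported and none is singled out.
- Report the number of patients scored at each time point, since section 9.3 allows for withdrawals and loss to follow-up.
- In sections 8.2 and 8.3, drop the word *significant* or state its criterion before data review.
- Make the pain time points agree between the synopsis and section 8.6.

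Under section 11.1 this takes a short signed amendment with IRB approval before implementation. It adds no patients, visits or data collection.

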### 15.1 Determination of Sample Size

As this is a feasibility study, no formal sample size estimation is performed. A sample of 30 will be sufficient to test feasibility and patient reported outcomes.

### 16 Investigator Responsibilities

The Investigator will be able to publish and/or present the data generated from the study after mutual agreement between the Investigator and Sponsor. The Investigator will provide the sponsor with a manuscript copy of the abstract and paper at least 60 days in advance of presentation to editors for publication or presentation.

### 16.1 Ethics Committee Approval/IRB

The investigator/co-investigator is responsible for the submission to the central/local IRB.

The content of the submitted documents must be documented in writing. A copy of this document will be provided to Medela AG. A copy of the IRBopinion/approval together with the

list of IRB voting members will be provided to Medela AG (or designee) prior to initiating the clinical investigation at a particular site.

The investigator is obliged to submit the appropriate documentation if any necessary extension or renewal of the IRB approval has to be obtained.

The investigator must report to the IRB any new information that may affect the safety of the subjects or the conduct of the clinical investigation.

Upon completion of the clinical investigation, the investigator shall provide the IRB with a brief report of the outcome of the clinical investigation as required by the local IRB.

### 16.2 Study conduct

Prior to shipment of the first clinical investigation device and first implantation, the investigator must read and sign this CIP as well as the Investigator's Agreement, to document that he/she has accepted to conduct the clinical investigation according to all agreed conditions and follow the CIP.

Prior to enrolling any subjects in the clinical investigation, all national and local regulatory requirements must be fulfilled.

Each clinical investigation site must have, but is not limited to, the following documents:

- Competent authority approval, if applicable
- Ethics committee approval
- Signed investigator's agreement
- Signed and dated CVs for all investigators participating in the clinical investigation.
- Laboratory Accreditation and the normal ranges

### 16.3 Regulatory Reporting

The investigator is obliged to report in writing to the IRB, any Serious Adverse Event whether device related or not within the timelines required by the IRB. Investigator is obliged to report in writing to the CA if applicable, any Serious Adverse Event whether device related or not within the timelines required by the CA and inform Medela about this report.

### 17 Sponsor Responsibilities

Investigator is responsible to apprehend the approval from the Competent Authority (CA), if applicable, prior to any site initiation. Investigator must report to the CA any new information that may affect the safety of the subjects or the conduct of the clinical investigation and inform Medela about this report

### 17.1 Subject Insurance

Subjects who participate in this study will be insured against study related injury according to local regulatory requirements. Medela AG has issued clinical trial liability insurance with appropriate coverage for the continuation of the entire study.

### **17.2 Compliance statements**

This clinical investigation is designed to be performed in accordance with the Declaration of Helsinki 2008, ISO 14155:2011(E), ICH-GCP, Local and National regulations.

Any corrections to the CIP that might become necessary to be in conformity with new standards and regulations will be issued as amendments to this CIP. This clinical investigation shall not begin until the required approvals from the IRBs and the applicable regulatory

### 18 Audits and inspections

An internal audit is performed by the Institution and its employees. Prior to the internal audit, Medela and the Institution shall jointly agree on the scope and plan of the audit. During the internal audit, the Institution shall gather and evaluate all records, information and documentation within the scope of the audit and, if necessary, conduct interviews with the Institution's and/or subcontractor's employees. It shall inform Medela regularly about progress and developments of the audit. At the end of the audit, the Institution shall issue a final report and hand it over to Medela.

An external audit is performed by Medela or third parties acting on behalf of Medela with confidentiality obligations, i.e. auditors and external counsel. Prior to the external audit, Medela and the Institution shall jointly agree on the scope and plan of the audit. During the external audit, the Institution has comprehensive obligations to cooperate, including but not limited to making available all records, information and documentation within the scope of the audit, handing over documents (hard copies and electronic documents) and allowing Medela or the third party acting on behalf of Medela to conduct interviews with the Institution's employees.

### **19** Publication policy

The Institution has the sole right to the primary presentation and publication of the Study Results, including articles, papers, posters, abstracts, presentations, etc. ("Publication"). Before Publication of the Study Results, the Institution or the Principal Investigator shall submit the manuscript to Medela and Medela shall have a period of sixty (60) days to review the proposed Publication for the disclosure of patentable inventions of interest to Medela and for any information considered proprietary or Confidential Information by Medela. If a patentable invention of interest to Medela is to be disclosed, the Publication shall be delayed to permit Medela to prepare and file a patent application in timely manner. Publication may not be delayed more than an additional ninety (90) days to permit the preparation and filing of a patent application. If proprietary or Confidential Information of Medela are in the manuscript, the Publication shall require approval by Medela before submission to the presenter or publisher. The Institution and the Principal Investigator shall have sole responsibility for the scientific content of the Publications. The Parties agree that Publications should be made in the first place in prestigious scientific periodicals (peer reviewed), in books or at congresses and conferences.

